7.6.8 Clinical Laboratory Evaluations

Clinical laboratory parameters (hematology, serum chemistry) will be evaluated.

[REDACTED]

[REDACTED]

[REDACTED]

[REDACTED]

7.6.11 Pregnancy Testing

By-subject listing of pregnancy tests results will be provided for all treated female subjects.

[REDACTED]

[REDACTED]

[REDACTED]

[REDACTED]

8 CONVENTIONS

The following conventions may be used for imputing partial dates for analyses requiring dates:

For death dates, the following conventions will be used for imputing partial dates:

- If only the day of the month is missing, the 1st of the month will be used to replace the missing day. The imputed date will be compared to the last known date alive and the maximum will be considered as the death date.
- If the month or the year is missing, the death date will be imputed as the last known date alive

- If the date is completely missing but the reason for death is present, then the death date will be imputed as the last known date alive

For date of progression, the following conventions will be used for imputing partial dates:

- If only the day of the month is missing, the 1st of the month will be used to replace the missing day.
- If the day and month are missing or a date is completely missing, it will be considered as missing.

In cases where the date of death is present and complete, the imputed progression date will be compared to the date of death. The minimum of the imputed progression date and date of death will be considered as the date of progression.

For missing and partial adverse event onset dates, imputation will be performed using the Adverse Event Domain Requirements Specification³.

For missing and partial adverse event resolution dates, imputation will be performed as follows:

If only the day of the month is missing, the last day of the month will be used to replace the missing day

- If the day and month are missing or a date is completely missing, it will be considered as missing.

Missing and partial non-study medication domain dates will be imputed using the derivation algorithm described in 4.3.3 of BMS Non-Study Medication Domain Requirements Specification⁴.

For other partial/missing dates, the following conventions may be used:

- If only the day of the month is missing, the 15th of the month will be used to replace the missing day.
- If both the day and the month are missing, “July 1” will be used to replace the missing information.
- If a date is completely missing, it will be considered as missing.

The following conversion factors will be used to convert days to months or years: 1 month = 30.4375 days and 1 year = 365.25 days.

Duration (e.g. time from first diagnosis to first dosing date, duration of response, and time to response) will be calculated as follows:

$$\text{Duration} = (\text{Last date} - \text{first date} + 1)$$

All statistical analyses will be carried out using SAS (Statistical Analysis System software, SAS Institute, North Carolina, USA) unless otherwise noted.

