8.1.1 Post Study Treatment Study Follow-up

Participants who discontinue study treatment before 24 weeks will be followed for 100 days after the last dose of nivolumab or for a total of 26 weeks from first on-study treatment with nivolumab whichever is earliest.

Participants who continue to benefit clinically from nivolumab at 26 weeks will continue treatment via commercial supply (provided by BMS) as long as clinical benefit is observed or until treatment is no longer tolerated by the participant. AEs/SAEs for participants receiving commercial supply will be reported via spontaneous reporting.

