8.3 Lost to Follow-Up

- All reasonable efforts must be made to locate participants to determine and report their ongoing status. This includes follow-up with persons authorized by the participant.
- Lost to follow-up is defined by the inability to reach the participant after a minimum of **three** documented phone calls, faxes, or emails as well as lack of response by participant to one registered mail letter. All attempts should be documented in the participant's medical records.
- If it is determined that the participant has died, the site will use permissible local methods to obtain date and cause of death.
- If investigator's use of third-party representative to assist in the follow-up portion of the study has been included in the participant's informed consent, then the investigator may use a Sponsor retained third-party representative to assist site staff with obtaining participant's contact information or other public vital status data necessary to complete the follow-up portion of the study.
- The site staff and representative will consult publicly available sources, such as public health registries and databases, in order to obtain updated contact information.
- If after all attempts, the participant remains lost to follow-up, then the last known alive date as determined by the investigator should be reported and documented in the participant's medical records.

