7.6.1 Deaths

Deaths will be summarized by tumor type:

- All deaths, reasons for death
- Deaths within 100 days of last dose received or for a total of 26 weeks from first on-study treatment with nivolumab whichever is earliest, reasons for death

By-subject listing of deaths will be provided for the all enrolled subjects population.

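### When the month of death is missing, SAP 8 ignores a recorded year, which can overstate deaths inside the safety window

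*SAP*

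**What the plan says.** SAP 8 opens its date conventions permissively, but the death-date block is firm: "For death dates, the following conventions will be used for imputing partial dates". Three cases follow.

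- Only the day is missing: the first of the recorded month is used, and then "The imputed date will be compared to the last known date alive and the maximum will be considered as the death date". The recorded month and year are kept, with the last known alive date as a floor.
- Month or year missing: "If the month or the year is missing, the death date will be imputed as the last known date alive". No comparison is made with a year that was recorded.
- Nothing recorded: where "If the date is completely missing but the reason for death is present", the last known alive date is used again.

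SAP 7.6.1 plans two death summaries. One is "All deaths, reasons for death". The other is "Deaths within 100 days of last dose received or for a total of 26 weeks from first on-study treatment with nivolumab whichever is earliest". Only the second needs the date of death.

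Under Protocol 8.1.1, participants who stop treatment early "will be followed for 100 days after the last dose of nivolumab or for a total of 26 weeks from first on-study treatment", whichever comes first. Planned contact therefore ends at about the point where the window closes.

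**The concern.** The first two cases treat recorded information differently. With the day missing, what was recorded is respected. With the month missing, a recorded year counts for nothing, and the record is handled as if no date existed. The SAP 8 rule for other dates with day and month missing does keep the recorded year, by using 1 July.

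The result can be a death date that the record excludes. Because planned contact stops near the end of the window, the last known alive date will usually fall inside it, and the death inherits that status. A death known to have occurred in a later calendar year, after the window closed, would then be reported as a death within the window.

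At stake is a descriptive count in a single-arm safety study with no hypothesis test. With 30 RCC participants, one misplaced death is visible in the table.

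**Working it through.** The documents give no figure for in-window deaths or partial death dates, so there is nothing to reproduce. The check is date logic on invented dates.

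**Inputs**
- Window end = the earlier of (last dose + 100 days) and (first dose + 182 days), from SAP 7.6.1.
- Current imputed date, month missing = last known alive date, from SAP 8.
- Earliest date the record allows = the later of 1 January of the recorded year and the last known alive date.
- Planned denominators: 70 NSCLC, 30 RCC, 100 pooled, from SAP 5.

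**Worked cases**
- Case A, wrong count. First dose 1 Feb 2019, last dose 1 May 2019, last known alive 1 Aug 2019, death recorded only as 2020. Last dose + 100 days is 9 Aug 2019 and first dose + 182 days is 2 Aug 2019, so the window ends 2 Aug 2019. The rule gives 1 Aug 2019: in window. The earliest possible date is 1 Jan 2020, and 0 of 366 possible dates are in the window.
- Case B, open. First dose 1 Sep 2019, last dose 1 Nov 2019, last known alive 1 Dec 2019, death in 2020. The window ends 9 Feb 2020. The rule gives in window. Of the 366 possible dates, 31 + 9 = 40 (10.9%) are in the window, so the count may be right.
- Case C, no error. First dose 1 Mar 2019, last dose 1 Apr 2019, last known alive 15 Sep 2019, death in 2020. The window ended 10 Jul 2019, and the rule already gives out of window.
- Case D, same year. As Case A, but death recorded as 2019. The later of 1 Jan 2019 and 1 Aug 2019 is 1 Aug 2019, so old and new rules agree on in window, although only 2 of 153 possible dates (1 Aug to 31 Dec) are inside it.

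**Direction.** The last known alive date is the earliest possible date of death. Moving a death to its earliest possible date can bring it into a window that is bounded above, but cannot take it out.

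**How often the year settles the matter.** This enumeration uses assumed, equally weighted scenarios: first dose on each day of one year, 1 to 12 doses, last known alive date weekly from last dose to window end, and recorded year one later than the last-alive year. That gives 54,750 scenarios.
- Current rule: 100% in window. This holds by construction, since the last-alive date was placed there.
- Later of 1 January and last known alive date: 12.3% in window. In the other 87.7% the recorded year alone proves the death came after the window.
- If the true date is uniform over the recorded year, about 1.1% would truly be in the window.

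**How often the year differs at all.** Assume last-alive dates are spread evenly over the year. The chance that death falls in a later calendar year is then the mean gap divided by 365 days. For gaps of 1 to 365 days it is 183/365 = 0.50; for gaps of 1 to 182 days it is 91.5/365 = 0.25. So 50% to 75% of month-missing post-window deaths would look like Case D, which the new imputation does not change.

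**Size per death.** 100/100 = 1.0 point pooled, 100/70 = 1.4 in NSCLC, 100/30 = 3.3 in RCC. Three such deaths, an assumed upper figure, would add 3.0, 4.3 or 10.0 points if all fell in that column.

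**The case against.** The strongest reply is that the triggering record should be rare. No survival follow-up is scheduled beyond the window. Protocol 9.2.1 does not oblige investigators to look for events in former participants, and events on commercial supply go to spontaneous reporting. Participants on treatment are seen every two weeks, and SAEs are due to the sponsor within 24 hours. Protocol 8.3 adds: "If it is determined that the participant has died, the site will use permissible local methods to obtain date and cause of death". All of this stands. It makes the expected number small but not zero: tracing of participants lost to follow-up can return a year alone, and the all-deaths line provides a place for such deaths.

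It can also be said that the rule errs on the inclusive side, which is tolerable in a safety study, and that a by-subject death listing allows individual review. That is a fair defence where the date is unknown. It does not justify overriding a year that is known. Whether the listing will mark imputed dates cannot be seen, because the mock-ups are in the Data Presentation Plan.

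A reader might infer more than the documents support:
- That every death with a missing month or year is placed wrongly. If the year is missing, or nothing is recorded, there is no recorded year to contradict.
- That such deaths always land inside the window. A last-alive date can fall after it, as in Case C. The follow-up visit tolerances alone reach day 30 + 5 + 70 + 5 = 110 after last dose.
- That an in-window classification of a later-year death is always wrong. A window crossing New Year can make it right, as in Case B.
- That deaths are made to look close to an infusion. The last-alive date may be up to 100 days after the last dose and still in the window, so this does not follow.

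**Conclusion.** The rule is wrong as written in one defined situation: the year of death is recorded, the month is missing, and the year is later than that of a last known alive date inside the safety window. The imputed date then contradicts the record, and the in-window count in SAP 7.6.1 can be too high. It cannot be too low, provided the last known alive date is itself correct.

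The consequence is minor. Deaths are neither a primary nor a secondary endpoint, so it would be too strong to call the in-window count a main result of the study. The number of affected records is unknown, and any figure for it, including the range of 0 to 3 used here, is an assumption. The per-death shifts rest on the planned denominators; the numbers actually treated may differ. The percentages from the enumeration describe assumed scenarios and do not forecast this trial.

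**What to change.** Split the second death-date rule in SAP 8:

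- Year recorded, month missing: use the later of 1 January of the recorded year and the last known alive date. This extends the logic of the day-missing rule.
- Year missing: keep the last known alive date, as now. The rule for a completely missing date also stays.

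This corrects Case A but leaves Cases B and D in the window, so a presentation change is needed as well. Flag imputed death dates in the by-subject listing. In SAP 7.6.1, show in-window deaths with and without those whose recorded date parts leave membership open. Membership is settled when the earliest and latest dates compatible with the record fall on the same side of the window end, and open otherwise.

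The cost is one reworded rule, a flag and one extra line in the death table. The downside is that the in-window count may appear as a range.

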9 CONTENT OF REPORTS

All analyses described in this SAP will be included in the Clinical Study Report except where otherwise noted. Refer to the Data Presentation Plan for mock-ups of all tables and listings.

APPENDIX 1 SCHEDULE OF ACTIVITIES

Table 2-1: CA209887 Screening procedures and assessments

Procedure	Screening Visit	Notes
		Screening visit will occur within 28 days before start of nivolumab
Eligibility Assessments		
Informed Consent	X	
IVRS	X	An Interactive voice recognition system (IVRS) will be used to assign participant numbers.
Inclusion/Exclusion Criteria	X	
Medical History	X	Medical history will include smoking history, and comorbidities. Mutation status of EGFR and ALK will be collected if available. Additional biopsies for mutation status, if not previously tested, are not required.
Safety Assessments		
Physical Examination	X	Includes height, weight, and ECOG PS (Appendix 1). Full physical exam required at baseline.
Vital Signs	X	Temperature, BP, HR, RR. Obtain vital signs at screening visit and within 72 hours of first dose.
Assessment of Signs and Symptoms	X	After obtaining Informed Consent, assess all signs and symptoms within 14 days of first dose, prior to study treatment initiation.
Concomitant medications	X	Within 14 days of first dose.
Laboratory Tests	X	Laboratory Tests performed locally within 14 days prior to first dose (unless otherwise specified): CBC with differential, serum chemistry (BUN or serum urea level, serum creatinine, sodium, potassium, calcium, magnesium, phosphate, chloride, and glucose), liver function tests (AST, ALT, total bilirubin, alkaline phosphatase, albumin, LDH), TSH, free T3, free T4 (within 28 days prior to first dose), hepatitis B surface antigen (HBsAg) and hepatitis C antibody (HCV Ab) or HCV RNA.
Pregnancy Test	X	Within 24 hours prior to first dose for WOCBP only (serum or urine at the site).

ALT = alanine aminotransferase, AST = aspartate aminotransferase, BP = blood pressure, BUN = blood urea nitrogen, CBC = complete blood count, ECOG = Eastern Cooperative Oncology Group, HR = heart rate, LDH = lactate dehydrogenase, NCI CTCAE = National Cancer Institute Common Terminology Criteria for AEs, RR = respiratory rate, TSH = thyroid stimulating hormone, T3 = triiodothyronine, T4 = thyroxine, WOCBP = Women of Childbearing Potential

Table 2-2: CA209887: On-Study Procedures and assessments

Procedure	Each Cycle (Every 2 weeks)	Notes
Safety Assessments		
Physical Measurements (including Performance Status)	X	Collect weight and ECOG Performance Status (Appendix 1) within 72 hours prior to dosing. Targeted physical examination may be performed if clinically indicated and is recommended to include cardiovascular, gastrointestinal, pulmonary and neurological exam for participants with brain metastases.
Vital Signs	X	Within 72 hours prior to dosing, tests includes temperature, BP, HR and RR
Serious Adverse Event Assessment	X	Assessed using NCI CTCAE v 4.0 (continuously monitored throughout treatment period)
Adverse Events Assessment	X	Assessed using NCI CTCAE v 4.0(continuously monitored throughout treatment period)
Review Concomitant Medication	X	
Laboratory Tests	X ^{a, b, c, d}	CBCs with differential ^a Serum chemistry tests ^b and liver function tests ^c should be checked every cycle, and the results should be obtained prior to dosing. Thyroid Function Test (TFTs) ^d should be checked every 6 weeks.
Pregnancy Test	Every 4 weeks	Completed more frequently if required by local standards (serum or urine as required by standard of care at the site).
Clinical Drug Supplies		
Administration of nivolumab (3 mg/kg)	X	All enrolled participants continue treatment every 2 Weeks. Treatment should be continued as long as clinical benefit is observed for a maximum of 24 weeks or until treatment is no longer tolerated by the participant or withdrawal of consent. Record Study Drug Infusion start and stop

BP = blood pressure; CBC = complete blood count; ECOG = Eastern Cooperative Oncology Group; HR = heart rate; LDH = lactate dehydrogenase; NCI CTCAE = National Cancer Institute Common Terminology Criteria for AEs; RR = respiratory rate.

^a CBCs with differential includes white blood cell count, lymphocyte count, absolute neutrophil count, hemoglobin, hematocrit, and platelet count. Results to be obtained prior to dosing on infusion days.

^b Serum chemistry tests include blood urea nitrogen (BUN) or serum urea level, serum creatinine, sodium, potassium, calcium, magnesium, phosphate, chloride, and glucose.

^c Liver function tests include AST, ALT, total bilirubin, alkaline phosphatase, albumin, LDH.

^d Thyroid function testing including TSH (reflex to free T3 and free T4 if abnormal result).

Table 2-3: CA209887: Follow-up Procedures

Procedure	Follow-up phase	Notes
	Follow-up Visit 1: 30 days (+/- 5 days) after last dose or on the date of discontinuation (+/- 5 days) if date of discontinuation is greater than 35 days after last dose. Follow up Visit 2: 70 days (+/- 5 days) after Follow up Visit 1.	Participants who discontinue on-study treatment with nivolumab before 24 weeks will be followed for 100 days after the last on-study dose of nivolumab or for a maximum of 26 weeks from the date of the first on-study dose of nivolumab, whichever occurs earliest.
Safety Assessments		
Physical measurements	X	Collect weight and ECOG Performance Status. Focused physical examination may be performed if clinically indication.
Vital Signs	X	Temperature, BP, HR and RR.
Adverse Events Assessment	X	
Serious Adverse Event Assessment	X	All SAEs after 26 weeks of study duration for participants on commercial nivolumab supply will be reported to India Health Authority as part of spontaneous reporting.
Review Concomitant Medication	X	
Laboratory Tests	X	Laboratory tests as listed for on treatment assessment in Table 2-2.
Pregnancy Test	X	Completed more frequently if required by local regulations (serum or blood as required by standard of care at the site).

BP = blood pressure; ECOG = Eastern Cooperative Oncology Group; HR = heart rate; RR = respiratory rate.

Table 7.6-1: Select Adverse Events

Category	Subcategory	Preferred Terms
Endocrine Adverse Events	ADRENAL DISORDER	ADRENAL INSUFFICIENCY
		ADRENAL SUPPRESSION
		BLOOD CORTICOTROPHIN DECREASED
		BLOOD CORTICOTROPHIN INCREASED
	DIABETES	DIABETES MELLITUS
		LATENT AUTOIMMUNE DIABETES IN ADULTS
	PITUITARY DISORDER	HYPOPHYSITIS
	THYROID DISORDER	AUTOIMMUNE THYROIDITIS
		BLOOD THYROID STIMULATING HORMONE DECREASED
		BLOOD THYROID STIMULATING HORMONE INCREASED
		HYPERTHYROIDISM
		HYPOTHYROIDISM
		SECONDARY ADRENOCORTICAL INSUFFICIENCY
THYROID FUNCTION TEST ABNORMAL THYROIDITIS		
THYROXINE DECREASED		
THYROXINE FREE DECREASED		

Category	Subcategory	Preferred Terms
		THYROXINE FREE INCREASED THYROXINE INCREASED TRI-IODOTHYRONINE INCREASED
Hypersensitivity/Infusion Reactions		ANAPHYLACTIC REACTION HYPERSENSITIVITY INFUSION RELATED REACTION
Gastrointestinal Adverse Events		COLITIS DIARRHOEA ENTERITIS ENTEROCOLITIS FREQUENT BOWEL MOVEMENTS GASTROINTESTINAL PERFORATION
Hepatic Adverse Events		ACUTE HEPATIC FAILURE ALANINE AMINOTRANSFERASE INCREASED ASPARTATE AMINOTRANSFERASE INCREASED BILIRUBIN CONJUGATED INCREASED BLOOD BILIRUBIN INCREASED HEPATIC ENZYME INCREASED HEPATIC FAILURE HEPATITIS HYPERBILIRUBINAEMIA LIVER DISORDER LIVER FUNCTION TEST ABNORMAL

Category	Subcategory	Preferred Terms
		TRANSAMINASES INCREASED
Pulmonary Adverse Events		ACUTE RESPIRATORY DISTRESS SYNDROME ACUTE RESPIRATORY FAILURE INTERSTITIAL LUNG DISEASE LUNG INFILTRATION PNEUMONITIS
Renal Adverse Events		BLOOD CREATININE INCREASED CREATININE RENAL CLEARANCE DECREASED HYPERCREATININAEMIA NEPHRITIS NEPHRITIS ALLERGIC RENAL FAILURE RENAL FAILURE ACUTE RENAL TUBULAR NECROSIS TUBULOINTERSTITIAL NEPHRITIS
Skin Adverse Events		BLISTER DERMATITIS DERMATITIS EXFOLIATIVE DRUG ERUPTION ECZEMA ERYTHEMA EXFOLIATIVE RASH PALMAR-PLANTAR ERYTHRODYSAESTHESIA SYNDROME

Category	Subcategory	Preferred Terms
		PHOTOSENSITIVITY REACTION
		PRURITUS
		PRURITUS ALLERGIC
		PRURITUS GENERALISED
		PSORIASIS
		RASH
		RASH ERYTHEMATOUS
		RASH GENERALISED
		RASH MACULAR
		RASH MACULO-PAPULAR
		RASH PAPULAR
		RASH PRURITIC
		SKIN EXFOLIATION
		SKIN IRRITATION
		URTICARIA
Neurological toxicity		NEUROTOXICITY

Source: MedDRA version 16

[REDACTED]

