7.6.5 Select Adverse Events

Unless otherwise specified, analyses will be performed by select AE category. Some analyses may also be repeated by subcategory of endocrine events.

Select AEs includes:

- Pulmonary toxicity
- Gastrointestinal toxicity (diarrhea or colitis)
- Endocrinopathies
- Hepatotoxicity (including asymptomatic LFT elevations)
- Renal toxicity
- Skin toxicity
- Neurological toxicity
- Hypersensitivity/infusion reactions

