7.6.5.1 Incidence of Select AE

Select AEs (see Table 7.6-1) will be summarized by tumor type for each category/subcategory for all treated subjects.

- Overall summary of any select AEs by worst CTC grade (grade 1, 2, 3, 4, 5, unknown) presented by Category or Subcategory/PT.
- Overall summary of drug-related select AEs by worst CTC grade (grade 1, 2, 3, 4, 5, unknown) presented by Category or Subcategory/PT.
- Summary of frequency of unique select AEs

The analyses will be conducted using the 100-day or for a total of 26 weeks from first on-study treatment with nivolumab whichever is earliest safety window.

By-subject select AE listing will be provided.

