7.6.7 Immune Mediated Adverse Events

In order to further characterize AEs of special clinical interest analysis of immune-mediated AEs (IMAE) will be conducted. Immune-mediated AEs are specific events (or groups of PTs describing specific events) that include pneumonitis, diarrhea/colitis, hepatitis, nephritis/renal dysfunction, rash, endocrine (adrenal insufficiency, hypothyroidism/thyroiditis, hyperthyroidism,

diabetes mellitus, and hypophysitis), and other specific events, considered as potential immune mediated events by investigator, that meet the definition summarized below:

- those occurring within 100 days of the last dose or for a total of 26 weeks from first on-study treatment with nivolumab whichever is earliest
- regardless of causality,
- treated with immune-modulating medication (of note, endocrine Adverse events such as adrenal insufficiency, hypothyroidism/thyroiditis, hyperthyroidism, diabetes mellitus, and hypophysitis are considered IMAEs regardless of immune-modulating medication use, since endocrine drug reactions are often managed without immune-modulating medication).

For the most recent studies, the data collection for IMAE was modified to also collect data on investigator assessment of potential IMAE including evidence of immune mediated etiology. For these studies (which will be clearly identified as such in the study specific SAP), an additional criteria accounting for immune mediated etiology or immune mediated component is also to be considered:

- with no clear alternate etiology based on investigator assessment, or with an immune mediated component

The list of MedDRA preferred terms used to identify Immune-Mediated adverse events is revisited quarterly and updated accordingly. The preferred terms used for the selection at the time of the database lock by categories will be provided.

IMAEs will be summarized for each immune mediated category / PT using the 100 days of the last dose or for a total of 26 weeks from first on-study treatment with nivolumab whichever is earliest:

- Overall summary of AEs by worst CTC grade (grade 1, 2, 3, 4, 5, unknown) presented by immune mediate Category/ PT. This summary includes all AEs that are qualified for IMAE preferred terms list, without requirement of either usage of immune modulating medications or accounting for immune mediated etiology or immune mediated component. .

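### SAP Table 7.6-1 files secondary adrenocortical insufficiency as a thyroid event, so any reported case would be counted in the wrong endocrine subtotal (minor)

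*SAP*

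**What the plan says.** SAP Table 7.6-1, printed after the schedule of activities in Appendix 1, assigns preferred terms to select-AE categories. Only the endocrine category has subcategories:

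- "ADRENAL DISORDER": adrenal insufficiency, adrenal suppression, and corticotrophin decreased and increased.
- Diabetes: two terms.
- "PITUITARY DISORDER": hypophysitis only.
- "THYROID DISORDER": the thyroid conditions and thyroid laboratory terms, and among them "SECONDARY ADRENOCORTICAL INSUFFICIENCY".

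SAP 7.6.5.1 cites this table as the source for the select-AE summaries and commits to them for each category and subcategory in all treated participants. The summary that serves the secondary endpoint is specified as "Overall summary of drug-related select AEs by worst CTC grade (grade 1, 2, 3, 4, 5, unknown) presented by Category or Subcategory/PT". SAP 7.6.5 is more tentative: "Some analyses may also be repeated by subcategory of endocrine events". Neither document corrects the placement of the term.

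**The concern.** The term names the adrenal cortex, and the same table has a subcategory for adrenal events. A program that follows the table would add a participant with this term to the thyroid subtotal, at that participant's worst grade, and would leave the adrenal or pituitary subtotal without them.

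Safety is the only objective of this study, and endocrinopathies are one of the named select-AE groups in the secondary endpoint (SAP 4.2; protocol 10.3.2.2). Subcategory counts are likely to be small, so a single misplaced participant can decide whether a subtotal reads zero. A reader who takes only the subtotals from the report would be given the wrong organ.

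**Working it through.** **Is the placement real?** In the thyroid block the term follows hypothyroidism and precedes the abnormal thyroid function test term, which is its correct alphabetical position. Eight other preferred terms separate it from the last adrenal term. A row displaced by accident would be unlikely to land in its alphabetical slot. The cell layout of the text copy does break just after this row, where two thyroid terms share a cell, so the PDF page deserves a glance.

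**Where does the table's own logic put it?** The adrenal block holds adrenal insufficiency and also "BLOOD CORTICOTROPHIN DECREASED", so the table treats corticotrophin findings as adrenal. That favours the adrenal block. The pituitary block is arguable, because the word secondary points to a cause upstream of the adrenal gland. The table gives no basis for the thyroid block.

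**Size of the shift.** The plan states no figure on this point, so there is none to reproduce. The inputs are the planned numbers in SAP section 5: 70 NSCLC, 30 RCC, 100 pooled. I assume that all enrolled participants are treated and that the affected participant has no other term in the subcategories concerned. The shift per participant is 1/n:

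| Column | n | Thyroid subtotal too high by | Adrenal (or pituitary) subtotal too low by |
|---|---|---|---|
| NSCLC | 70 | 1/70 = 1.4 points | 1.4 points |
| RCC | 30 | 1/30 = 3.3 points | 3.3 points |
| Pooled | 100 | 1/100 = 1.0 point | 1.0 point |

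If the participant also has a true thyroid term, the thyroid count does not change, but its worst grade can still be set by the misplaced event.

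**What one pooled case looks like.** I use the Clopper-Pearson method of SAP Table 5-1; as a check, 5/100 gives 1.64% to 11.28%, which matches that table. If the term belongs with the adrenal events and is the only one, the adrenal subtotal as filed reads 0/100, with upper limit 1 − 0.025^(1/100) = 3.6%. Filed as adrenal it reads 1/100, with interval 0.03% to 5.4%. These intervals are illustrative.

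**How likely is it to matter?** The documents give no rate for this term, so the rate p is an assumption. The chance of at least one case is 1 − (1 − p)^n:

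| Assumed true rate | RCC (30) | NSCLC (70) | Pooled (100) |
|---|---|---|---|
| 0.1% | 3.0% | 6.8% | 9.5% |
| 0.5% | 14% | 30% | 39% |
| 1% | 26% | 51% | 63% |
| 2% | 45% | 76% | 87% |

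**What does not move.** The endocrine category total is unchanged, because the term stays within that category. The primary endpoint is tabulated by system organ class and preferred term (SAP 7.6.4) and does not use Table 7.6-1. The by-subject listings still name the event.

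**The case against.** The strongest reply is that this is a clerical slip in a lookup table for a term that may never be reported. SAP 7.6.5 makes the category the default level and the endocrine subcategory repeats partly optional. Where subcategories are shown, the preferred term is printed beneath them, so a careful reader would see the adrenal term under the thyroid heading. No hypothesis test is planned, and no endpoint total changes. All of this stands, and it limits the severity. It does not justify the placement, because SAP 7.6.5.1 does commit to summaries at subcategory level and a subtotal can be quoted without the lines beneath it.

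A reader might go further in three ways that the documents do not support:

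- **That adrenal toxicity will be understated.** This requires that the term is reported and that it belongs in the adrenal block. If the sponsor regards it as pituitary, the pituitary subtotal is the one affected. Only the error in the thyroid subtotal holds under both choices.
- **That the table contradicts SAP 7.6.7.** That section does name adrenal insufficiency apart from the thyroid conditions, in a list that begins "endocrine (adrenal insufficiency, hypothyroidism/thyroiditis, hyperthyroidism". But it defines a different analysis, of immune-mediated events, with its own preferred-term list that is updated quarterly and is not in the documents. Where that list files this term cannot be checked.
- **That a severe adrenal event would be hidden.** The preferred-term row and the listings still identify it. Only the subcategory subtotal would mislead.

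**Conclusion.** The point holds in a limited form. Followed as written, the SAP would count a reported case of secondary adrenocortical insufficiency as thyroid toxicity in the subcategory summaries and omit it from the subcategory where it belongs. The error is 1.4 points in NSCLC, 3.3 in RCC and 1.0 pooled for each affected participant, given the planned denominators and no other term in those subcategories. It is zero if the term is not reported. The finding also assumes that the PDF shows the row where the text copy shows it, which the alphabetical order supports. Severity: minor.

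**What to change.** Before database lock, take the term out of the thyroid block of SAP Table 7.6-1 and place it in the adrenal block, in line with the table's handling of adrenal insufficiency and corticotrophin terms. If the sponsor prefers the pituitary block, record the reason in the SAP. Program the subcategory tables from the corrected list. The cost is one row in one table. Design, sample size, data collection and the primary analysis are not affected.
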